**Parents should be adequately trained on dosing procedure prior to administering the first dose.**

LT4 will be administered as a single daily oral dose.

LT4 should be administered on an empty stomach, one-half to one hour before breakfast and at least 4 hours before or after drugs known to interfere with LT4 absorption. The need for dose adjustments should be evaluated when regularly administering within an hour of certain foods that may affect LT4 absorption [soybean flour (infant formula), cottonseed meal, walnuts, dietary fiber] (Tirosint® SOL USPI, Synthroid USPI).

Tirosint®-SOL may be administered in water or directly into the mouth (Tirosint® SOL USPI).

- To administer Tirosint®-SOL in water, the contents of one single unit-dose ampule should be squeezed into a glass or cup containing water. The diluted Tirosint®-SOL should be stirred and all of it drunk immediately. The glass or cup should be rinsed with additional water and the contents drunk to ensure that the total dose is taken. Tirosint®-SOL should not be diluted in a medium other than water. The ampule should be opened and the solution prepared immediately before intake; or
- To administer Tirosint®-SOL directly (without water), it can either be squeezed into the mouth or onto a spoon and immediately consumed.

LT4 tablets should be administered to infants and children who cannot swallow intact tablets by crushing the tablet, suspending the freshly crushed tablet in a small amount (5 to 10 mL or 1 to 2 teaspoons) of water and immediately administering the suspension by spoon or dropper. The suspension should not be stored ([Synthroid USPI](#)).

### 13.1.3 ADDITIONAL DOSING INSTRUCTIONS

It is recommended that parents are educated, by trained personnel, on appropriate TH administration, the substances (e.g. iron, calcium, soy, fiber) that can interfere with TH absorption, the importance of adherence to the treatment plan, and the importance of periodic follow-up care ([AAP 2006](#), [Rose 2023](#), [Synthroid USPI](#), [Tirosint® SOL USPI](#)). Education will be provided as per SOC.

While LT4 intake is recommended on an empty stomach, one-half to one hour before breakfast, literature is quite consistent in stating that such a recommendation may be difficult to adhere to in infants ([LaFranchi 2011](#)). The most recent guidelines on CH, issued by ENDO-European Reference Network, suggest that, in contrast to adults, neonates, infants and children can be administered LT4 together with food (but with avoidance of soy protein and vegetable fiber). Importantly, LT4 should be administered at the same time every day, also in relation to food intake; while this approach can improve compliance, it ensures as constant as possible LT4 absorption and, with that, as good as possible LT4 dose titration ([Van Trotsenberg 2021](#)). The most recent AAP guidelines also suggest that LT4 tablets can be crushed and suspended in 2 to 5 mL (about 1 teaspoon) of human milk, nonsoy-containing formula, or water and also that LT4 can be administered at any time of day in infants and toddlers (morning or evening, with or without feeds), as long as the timing and manner of administration are consistent ([Rose 2023](#)).

For the present study, in order to standardize the mode of administration, parents of newly diagnosed neonates will be instructed to administer LT4 first thing in the morning, possibly before the first bottle or feeding.

Parents of infants already on LT4 treatment who will remain on LT4 tablets will not be asked to change their habits (in terms of administration time and interval to food intake) upon inclusion in the study if these are providing adequate replacement, in order to ensure constant LT4 absorption and not compromise compliance.

Parents of infants already on LT4 treatment assigned to Tirosint®-SOL will be advised at inclusion to administer Tirosint-SOL as first thing in the morning, possibly before the first bottle or feeding. If this is in contrast with their previous habits and those were providing adequate replacement, upon discussion with the Investigator, they may be allowed to choose between the new habit and the old one (in terms of administration time and interval to food intake), in order not to compromise compliance with the treatment.

The intake of simethicone, iron, calcium, soy and fiber at the time of L-T4 administration should be avoided as they can interfere with TH absorption. LT4 should not be mixed with these substances and their intake should be delayed by about 4 hours from LT4 ([Van Trotsenberg 2021](#), [AAP 2006](#), [LaFranchi 2011](#), [Rose 2023](#)) (see also **Section 13.2.5**).

Typically, the daily LT4 tablet is crushed and mixed with water, expressed breast milk, or formula. The resulting suspension is drawn up in a syringe and squirted into the cheek pad or put in an open nipple for the infant to suck ([LaFranchi 2011](#)). SOC instructions about how to administer LT4 tablets will be provided to parents of neonates newly diagnosed with CH.

For Tirosint-SOL, reference is made to the instructions provided in the USPI.

## **13.2 PREPARATION, HANDLING, STORAGE AND ACCOUNTABILITY**

### **13.2.1 PACKAGING AND LABELLING**

The Sponsor will supply Tirosint®-SOL in the FDA-approved commercial packaging with study-specific labelling. Tirosint®-SOL is commercially available in 30-count boxes. Each box contains 6 pouches with 5 ampules of Tirosint®-SOL in each pouch (30 total doses). Each box and ampule are color coded to help clearly identify the dosage strength of Tirosint®-SOL.

Study specific label on the pouch will not obscure the original commercial labelling (lot, expiry date, and storage conditions) and will report the following information:

- Name and address of the sponsor;
- Study number;
- Box number;
- Clinical Batch number; and
- For clinical trial use only.

Study specific label to be added to the box will not obscure the original labelling and will report the following information:

- Name and address of the sponsor;
- Study number;
- Box number;
- Subject Number;
- Clinical Batch number; and

- For clinical trial use only.

The box number is a unique identifier (X-NN-NNNN) on each box and pouch that includes a Letter (identifying the strength), 2-digit Number (identifying the packaging campaign), and 4-digit Number (identifying the box number).

**Table 4: Dose Identifier Key**

Letter Identifier	Color Identifier	Dose Strength
I	GREEN	13 mcg
A	ORANGE	25 mcg
B	DARK BLUE	37.5mcg
C	RED	44 mcg
D	WHITE	50 mcg
E	GREY	62.5 mcg
F	PURPLE	75 mcg
G	OLIVE	88 mcg
H	YELLOW	100 mcg

For example, A-01-0001 indicates that this contains the 25 mcg dose and is the first box of the first packaging campaign. The Subject Number on the carton will be left blank. The Subject Number must be written by the PI or designee.

### 13.2.2 PREPARATION ONSITE

Not applicable.

### 13.2.3 RECEIPT, STORAGE AND ACCOUNTABILITY

The PI or designee should inventory each shipment of Tirosint®-SOL, which should then be transferred to a secure, temperature-controlled storage area that is accessible only to delegated site personnel. A temperature-recording device will be used to monitor the temperature in the storage area for the duration of the study.

Tirosint®-SOL must be stored in the original container (closed pouch) at 20°C to 25°C (68°F to 77°F); excursions permitted to 15° - 30°C (59° - 86°F). Any temperature deviations should be recorded in the IP log and reported to the Sponsor to determine if the product can still be used.

TIROSINT®-SOL oral solution must be used within three (3) months after opening the pouch. The ampules must be kept in the pouch until ready to use as important information may be lost (i.e., manufacturer/distributor names and distributor contact phone number).

Unused IP will be returned to the Sponsor or destroyed on-site according to clinical site standard operating procedures (SOPs). The clinical monitor or Sponsor designee will determine when these activities should occur.

IP accountability will be supported through documentation of receipt, dispensing, return and destruction, and overall reconciliation of these activities. All observed discrepancies in IP usage should be documented and explained.

For subjects assigned to Tirosint®-SOL, at each in-clinic visit, each subject will receive a sufficient number of cartons to ensure the daily administration of the dose until the following planned in-clinic visit. During the following in-clinic visit, the subject's parent/guardian will bring back to the study site all cartons, pouches, ampules previously received (partially used pouches including unused ampules and unused cartons, pouches and ampules) and receive a new supply of the IP. Returned supplies will not be redispensed.

For subjects assigned to LT4 tablets, each subject will either receive a sufficient number of tablets to ensure the daily administration of the dose until the following planned in-clinic visit or will purchase it from a local pharmacy upon prescription. The study site personnel are responsible for recording the product name and strength into the electronic case report form (eCRF).

In special circumstances (e.g. TM visits, pandemic restrictions) the study drugs might be shipped directly to patient.

#### **13.2.4 PRECAUTIONS AND OVERDOSAGE**

Additional information concerning relevant precautions and the procedures to be undertaken in the event of overdose can be found in the [Tirosint® SOL USPI](#).

#### **13.2.5 CONCOMITANT MEDICATIONS**

Subjects will be allowed to receive any concomitant medication necessary for the treatment of pre-existing concomitant pathologies or for intercurrent diseases that are not exclusionary.

Exclusionary medications are:

- liothyronine, from two weeks prior to start of screening;
- combination of LT4 and liothyronine, and thyroid extracts, from four weeks prior to start of screening;
- anticonvulsants, as they increase degradation of LT4;
- chronic or long-term systemic glucocorticoids, as they may affect interpretation of TFTs (short term use of systemic glucocorticoids, as well as inhalatory or topical corticosteroids are allowed).

All concomitant medications will be recorded in the eCRF.

All medications used by a particular subject should be listed, reviewed, and approved by the PI or designee.

Drugs known to interfere with LT4 absorption (such as calcium carbonate, ferrous sulfate, bile acids sequestrants and ion exchange resins), as well as simethicone, should be administered at least 4 hours apart from Tirosint®-SOL or LT4 tablets.

Biotin has been reported to interfere with some immunoassays using a streptavidin-biotin complex, including TSH and FT4 and clearance from the blood is yet unknown. For this reason, information on the use of biotin should be collected in the eCRF and parents/guardian should be advised to withhold biotin supplementation for four days before each blood draw ([Charles 2018](#)).

Consumption of certain foods may affect LT4 absorption thereby necessitate adjustments in dosing. Soybean flour (infant formula), cottonseed meal, walnuts, and dietary fiber may bind and decrease the absorption of LT4 from the gastrointestinal tract. Grapefruit juice may delay the absorption of LT4 and reduce its bioavailability.

Care should be taken to avoid concomitant administration of soy and fiber.

### **13.2.6 CONTRAINDICATIONS**

TIROSINT®-SOL is contraindicated in subjects with:

- Hypersensitivity to glycerol, the inactive ingredient in TIROSINT®-SOL; and/or
- Uncorrected adrenal insufficiency.

### **13.2.7 RESCUE MEDICATION**

No rescue medications will be used in this study.

## **13.3 BLINDING, TREATMENT ALLOCATION AND RANDOMIZATION PROCEDURES**

This study will not be blinded, all study staff will know what treatment is assigned.

All eligible subjects will be randomly assigned at Visit 1. Subject randomization will be 2:1 (Treatment:Control) and stratified by site through an Integrated Web Response System (IWRS). Randomization will be stratified based on age:

- neonates newly diagnosed  $\leq 28$  days; and
- infants  $> 28$  days already on therapy with LT4.

## **13.4 EMERGENCY CODE AND UNBLINDING PROCEDURES**

This is an open study therefore unblinding procedures are not needed.

## **14 DISCONTINUATION/WITHDRAWAL**

### **14.1 DISCONTINUATION/WITHDRAWAL**

Participation will be discontinued for any of the following reasons:

- Voluntary subject/legally authorized representative withdrawal for any reason;
- PI's discretion;
- An AE, including onset or worsening of a concomitant illness, that is considered by the PI to be incompatible with continuation in the study;
- Administration of a drug that is not permitted according to the exclusion criteria;
- Failure to comply with the requirements of the protocol or major protocol deviation (e.g., inclusion error, evidence of noncompliance with exclusion/inclusion criteria during the study, subject misses study visits, failure to take assigned medication, or provide blood sample as required, etc.);
- Lost to follow-up; or
- Subject death.

Subjects whose parents or legal guardians provide informed consent, receive the IP and subsequently withdraw, or are withdrawn or discontinued from the study, will not be replaced.

### **14.2 PREMATURE TERMINATION**

The trial may be suspended temporarily or terminated prematurely if there are any relevant medical or ethical concerns, or if completing the trial is no longer practicable. If such action is taken, the reasons for terminating the trial must be documented in detail and submitted to the overseeing IRB. All subjects still under treatment at the time of termination will undergo a final examination and the results will be documented in the eCRF.

### **14.3 LOST TO FOLLOW-UP**

The PI or designee must take the following actions if a parent/guardian of a subject fails to return to the site for a required study visit:

- Attempt to contact the parent/ legal guardian and reschedule the missed visit as soon as possible; counsel parent/ legal guardian on the importance of maintaining the assigned visit schedule and ascertain if the subject wishes to and/or should continue in the study;
- Make every effort to regain contact with the parent/ legal guardian. Where possible, three (3) telephone calls should be made and, if necessary, a certified letter sent to the parent/legal guardian's last known mailing address. These contact attempts should be documented in the source documents and eCRF;

- Should the parent/legal guardian continue to be unreachable, they will be considered to have withdrawn from the study with a primary reason of lost to follow-up.

## 15 STUDY ASSESSMENTS AND PROCEDURES

### 15.1 EFFICACY ASSESSMENTS

#### 15.1.1 LABORATORY PARAMETERS

Laboratory parameters evaluated in this study include:

- Thyroid Stimulating Hormone (TSH);
- Free Thyroxine (FT4); and
- Total Thyroxine (TT4), optional, at the discretion of the Investigator.

The analyses will be conducted on serum samples.

Blood samples for serum FT4, TT4 and TSH monitoring will be collected 0 (during the visit) to - 7 days before each visit (within the allowed visit time frame) to allow for adequate time to evaluate the measurements.

Blood samples should be collected at least 4 hours after the last LT4 administration or before taking the LT4 daily dose ([VanTrotsenberg 2021](#), [Rose 2023](#)). Whenever possible perform the collection in the same way and at the same time at each visit.

At each visit, 1-4 mL of blood will be collected; 7-32 mL of blood will be collected per subject for the entire study (7-8 time points). If considering a maximum of two additional unscheduled visits during the course of the study, a maximum of 40 mL of blood will be collected over one year.

A venipuncture sample should be collected by accessing the veins of the antecubital fossa (inside the elbow), in order to obtain serum. If unable to obtain from antecubital fossa, a heel or finger prick is preferable to no sample. This must be clearly specified on the request to the laboratory and results will have to be converted by the laboratory to serum equivalents. In exceptional cases, a subject's blood draw may be performed at a different location (e.g. laboratory patient service center), as per SOC.

- Each site will attempt to use the same laboratory throughout the study (main laboratory). Additional laboratories may be used, but, in order to reduce variability, these should be limited to not more than 3 analytical lab facilities per site (e.g. hospital lab and other providers of diagnostic services such as Quest and LabCorp).
- Each site will attempt to use the same laboratory for the same subject throughout the study.
- Laboratory sampling and analytical procedures should be followed.

- Local lab reference ranges will be collected and any change in reference ranges should be recorded in the EDC.
- The laboratory assessments done for CH diagnostic purposes (routine newborns screening) are not part of this protocol (they precede screening/inclusion for the study). Results from the site's laboratory or other laboratories following different procedures are both acceptable.

When abnormalities in the laboratory parameters are detected, they will be assessed by the Investigator as clinically significant or not clinically significant. Because laboratory parameters are the main parameter of therapy monitoring and abnormalities are expected in relation to growth and the development of the disease and therapy, abnormalities will not be recorded in the subject's eCRF as medical history, nor as AEs, even when clinically significant.

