Von Heppe reported that in 28 newborns with primary CH, the initial dose necessary to normalize TSH is not lower when a liquid solution is used. The higher dose used in tablets is not due to inefficient absorption, but rather reflects the increased demand for TH in the first weeks of life. The liquid formula was easier to handle for the parents, and enabled more individualized dosage of newborns, especially those with a LBW. In comparison with parents whose children received LT4 in tablet form, the parents of newborns who received the liquid formula were more content with the treatment ([von Heppe 2004](#)).

Further knowledge on the use of LT4 oral solutions in the pediatric population has been gained recently.

A multicenter study compared the effectiveness of an LT4 oral solution (group D, 117 subjects) with that of a tablet formulation (group T, 137 subjects) in children with CH up to 3 years of age. Auxological parameters, LT4 dose and thyroid function values (TSH and FT4) at diagnosis, 3, 6, 12, 24, 36 months were not significantly different. TSH at 15 days ( $p = 0.002$ ) and 1 month ( $p = 0.009$ ) was significantly reduced in group D. At 2-year follow-up, median TSH was significantly lower in group T ( $p = 0.03$ ). Both therapeutic strategies were considered effective in the treatment of CH, with a higher risk of overtreatment in the first months of therapy associated with oral solution. No negative effects on cognitive development were observed ([Vigone 2021](#)).

A prospective randomized control study compared a liquid LT4 formulation available in Greece (Group B, 19 subjects) with tablets (Group A, 17 subjects) in the substitutive treatment of 3-12 years old children with CH, who were evaluated at 0, 2, 4 and 6 months. TSH values showed a statistically significant difference ( $p=0.017$ ) between groups only at 6 months (Group A having higher TSH levels than Group B), while FT4 levels had no statistical difference throughout the 6-month study period and were always within the normal range. Dose adjustments were more frequent in Group A ( $p=0.038$ ). Liquid LT4 substitutive treatment exhibited no statistically significant adverse effects in comparison to tablets ([Tzifi 2021](#)).

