## **17 ADVERSE EVENT DESCRIPTION AND REPORTING**

### **17.1 ADVERSE EVENTS (AEs)**

An AE is any untoward medical occurrence in a clinical trial subject, whether or not there is a suspected causal relationship between the event and the Study Drug. AEs include exacerbation of a pre-existing medical condition, that is, the condition has increased in severity, frequency and/or duration. A pre-existing condition that did not deteriorate during the study, but was treated with a medical or surgical procedure, should not be recorded as an AE. However, the procedure itself should be in the eCRF.

An adverse drug reaction (ADR) is any AE with a suspected causal relationship to the Study Drug. This means that there is at least reasonable evidence that the event might have been elicited by administration of the Study Drug.

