### **17.2 SERIOUS ADVERSE EVENTS (SAEs)**

SAEs are a subset of AEs that resulted in one of the following outcomes:

- Death;
- Life-threatening illness or injury (i.e. the patient was at risk of death at the time of the event; it does not refer to an event that hypothetically might have caused death if it were more severe);
- Inpatient hospitalization or prolongation of existing hospitalization;
- Persistent or significant disability or incapacity;
- A congenital anomaly or birth defect; or

- An important medical event (i.e. an event that jeopardize the patient or may require intervention to prevent one of the other outcomes listed above).

A serious adverse reaction (SAR) is any serious adverse event with a suspected causal relationship to the Study Drug. This means that there is at least reasonable evidence that the event might have been elicited by administration of the Study Drug.

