### 17.3 CAUSALITY ASSESSMENT AND CLASSIFICATION

The PI must make a causality assessment for each adverse event experienced by a study subject following at least one dose of Study Drug (IP) according to the following guidance. However, any adverse event that occurs between written informed consent and administration of the first dose of IP will be considered a pre-treatment adverse event (PTAE), and this option should be selected in the applicable form rather than making a causality assessment.

- Certain: There is clear evidence to suggest a causal relationship and other possible contributing factors can be ruled out. The clinical event, including laboratory test abnormality, occurs in a plausible time relationship to IP administration and cannot be explained by concurrent disease or other drugs or chemicals. The response to withdrawal of the drug (de-challenge) should be clinically plausible. The event must be pharmacologically or phenomenologically definitive, with use of a satisfactory re-challenge procedure if necessary.
- Probable: There is evidence to suggest a causal relationship and the influence of other factors is unlikely. The clinical event, including an abnormal laboratory test, occurs within a reasonable time after administration of the Study Drug, is unlikely to be attributed to concurrent disease or other drugs or chemicals, and follows a clinically reasonable response on withdrawal (de-challenge). Re-challenge information is not required to fulfil this definition.
- Possible: There is some evidence to suggest a causal relationship; however, other factors may have contributed to the event (e.g. the subject's clinical condition, other concomitant treatments). The clinical event, including an abnormal laboratory test, occurs within a reasonable time after administration of Study Drug, but could be explained by concurrent disease or other drugs or chemicals. Information on drug withdrawal may be lacking or unclear.
- Unlikely: There is another reasonable explanation for the event occurrence. A clinical event, including an abnormal laboratory test, whose temporal relationship to Study Drug administration makes a causal relationship improbable, and which other drugs, chemicals or underlying disease provide plausible explanations.
- Not related: There is no evidence of any causal relationship between the clinical event and Study Drug administration, and/or sufficient information exists to indicate that the event is related to another etiology.

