7.2 LABORATORY DATA

Only the following laboratory data will be collected:

- Thyroid Stimulating Hormone (TSH);
- Free Thyroxine (FT4); and
- Total Thyroxine (TT4), optional.

Analysis is described under section 6.1.2.

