9.4.2 Secondary efficacy analyses

Laboratory parameters (TSH and FT4)

Laboratory parameters (TSH and FT4) will be analysed at each time point by means of analysis of covariance (mixed model), including basal value, treatment group, age at randomization and interactions between visit and treatment group as covariate.

Normal distribution for TSH and FT4 will be tested with Shapiro Wilks, if data result not to be distributed as a normal distribution a log transformation will be applied.

The mixed model will be adjusted with Kenward-Roger method and the unconstructed covariance matrix will be used as first choice (other matrixes will be considered if there will be convergence problems).

Summary descriptive statistics will be provided for each laboratory parameter. TSH and FT4 levels at each visit will also be compared between treatment groups by Wilcoxon Mann-Whitney test. This analysis will also be repeated stratified on neonates and infants.

Laboratory data will also be listed with clinically significant information.

TSH values above 4.5 mU/L

The events of TSH values above 4.5 mU/L will be compared between treatment groups at each visit and aggregate from Visit 2 to the last available visit using a Chi-squared test or, when the expected values in any of the cells of a contingency table are below 5 or the total number of observations is less than 20, Fisher exact test as appropriate.

FT4 values below the middle of the laboratory normal range

The events of FT4 values below the middle of the laboratory normal range will be compared between treatment groups at each visit and aggregate from Visit 2 to the last available visit using a Chi-squared test or, when the expected values in any of the cells of a contingency table are below 5 or the total number of observations is less than 20, Fisher exact test as appropriate.

Parent satisfaction assessed by “Parents’ Satisfaction Questionnaire”

Parent satisfaction assessed by “Parents’ Satisfaction Questionnaire” score at V3, V5, V6, V7, V8, V9, V10, V11 will be analyzed by means of analysis of covariance (mixed model), including treatment age at randomization and interactions between visit and treatment group as covariate.

Normal distribution for Parents’ Satisfaction Questionnaire score will be tested with Shapiro Wilks, if data results not be distributed as a normal distribution a log transformation will be applied.

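### No planned table counts children with suppressed TSH or above-range FT4 by arm, although abnormal thyroid values are barred from AE recording and their significance rating reaches only a listing

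*Protocol*

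**What the plan says.** Protocol 15.1.1 covers TSH, FT4 and optional TT4. SAP 7.2 confirms that these are all the laboratory data there are: "Only the following laboratory data will be collected", followed by those three. When a value is abnormal, "they will be assessed by the Investigator as clinically significant or not clinically significant". Whatever the rating, it does not go into the "eCRF as medical history, nor as AEs, even when clinically significant". The stated reason is that these are the parameters by which therapy is monitored, and that abnormal values are expected with growth, disease and treatment. The section makes no exception for a value that meets a seriousness criterion or leads to withdrawal.

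Protocol 17 is written more broadly. Section 17.1 says "An AE is any untoward medical occurrence in a clinical trial subject". Section 17.2 says "SAEs are a subset of AEs that resulted in one of the following outcomes". The causality definitions in 17.3 refer to laboratory events, for example: "The clinical event, including laboratory test abnormality, occurs in a plausible time relationship to IP administration".

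In the SAP, the rating appears once, in 9.4.2: "Laboratory data will also be listed with clinically significant information". SAP Section 10, the safety analysis on the Safety Analysis Set (SAF), covers adverse events, vital signs, physical examination and compliance. It has no laboratory table. SAP 7.2 sends laboratory data to the efficacy variables, which 9.4.2 analyses on the Full Analysis Set (FAS).

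**The concern.** Levothyroxine can harm an infant in either direction. Protocol 9.1 lists effects of under-treatment on intellectual development and growth. For over-treatment it lists craniosynostosis, altered tempo of brain maturation and accelerated bone age. The protocol's own background points to over-treatment as the direction to watch with a liquid product. One prospective study in 42 newborns found significantly more suppressed TSH on liquid than on tablets. A larger multicenter comparison concluded that both forms were effective, "with a higher risk of overtreatment in the first months of therapy associated with oral solution".

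If abnormal values cannot become adverse events and no other table counts the low-TSH or high-FT4 side, a reader of the report could not see how many children in each arm were biochemically over-treated. An unremarkable AE table might then be read as reassurance on a point that it was never able to address.

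**Working it through.** The plan states no figure on this point, so the check sets the passages side by side.

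**Step 1: by-arm event counts.** Thyroid results can stray in four directions. SAP 9.4.2 provides the following:

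| Direction | Meaning | By-arm event count | Analysis set |
|---|---|---|---|
| High TSH | under-treatment | Yes: above 4.5 mU/L, each visit and aggregate from Visit 2 | FAS |
| Low FT4 | under-treatment | Yes: below mid-range, each visit and aggregate from Visit 2 | FAS |
| Low TSH | over-treatment | None | – |
| High FT4 | over-treatment | None | – |

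So 2 of 2 counts lie on the under-treatment side, 0 lie on the over-treatment side, and 0 of the 4 directions are counted on the SAF.

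**Step 2: other routes by which over-treatment could show.**
- *Level summaries, mixed models and Wilcoxon tests* (SAP 9.1, 9.4.2). A shift in the centre would appear, and the minimum, maximum and quartiles hint at the tails. They do not give the number of children outside range. Ranges differ by laboratory and age (protocol 11.2, 11.3.1), so a pooled minimum or quartile cannot be read against one limit.
- *Signs and symptoms.* Hyperthyroid signs are summarized separately, but the between-arm test is on children with at least one sign or symptom of either kind. A suppressed TSH without a recorded sign does not enter.
- *Dose re-adjustment.* Children needing a change in long-term follow-up are compared by arm, with no split into increases and decreases.
- *The listing.* It holds the values and the rating, but the reader must do the counting.

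**Step 3: the AE route.** Protocol 15.2.1 to 15.2.3 make clinically significant examination, vital-sign, growth and thyroid-sign findings adverse events when they arise after consent. The thyroid values are the one assessment treated differently. Because 17.2 makes serious events a subset of AEs, a thyroid value that on its own was considered an important medical event has no stated route to SAE reporting. SAP Section 4 defines an AE leading to discontinuation as an AE with the drug withdrawn. A withdrawal resting only on a thyroid value would therefore be missing from that row, although SAP 9.2 tabulates discontinuations with reasons.

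**Step 4: timing.** Screening closed on 31 March 2024 (SAP Section 3). Allowing 14 days of screening and 12 + 1.5 = 13.5 months of follow-up, the last child finished around the end of May 2025. The first SAP draft is dated 13 August 2025 and version 2.0 is dated 24 March 2026. A change to the recording rule can no longer affect conduct, but a change to the tables can still be made.

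**The case against.** The exemption is a reasoned choice. These values are efficacy endpoints in children who enter with elevated TSH at diagnosis, and recording every excursion as an AE would count the same thing twice. That stands, and nothing here asks for it to be undone.

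A reader might infer that the trial cannot show biochemical under-treatment. The documents do not support that. It is absent from the tables labelled safety, but SAP 9.4.2 counts and compares it by arm.

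A reader might also infer that serious harm escapes reporting. It does not in general. Most criteria in 17.2 are clinical outcomes, and a resulting clinical event remains an AE or SAE. What is left open is narrow: a thyroid value that alone is considered serious, or that alone ends participation.

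Nor do 15.1.1 and 17.3 flatly contradict each other. The exemption covers three named parameters, and routine monitoring continues outside the protocol (11.2). An abnormality in another test could still be an AE, so the laboratory wording in 17.3 has a use. The passages are unreconciled rather than incompatible.

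The background signal also has limits. The protocol does not say that those studies used the study product, and the multicenter study found lower median TSH on tablets at two years. Its over-treatment finding concerns the first months of therapy, whereas SAP 3.4 reports only 3 + 1 = 4 neonates, leaving 31 − 4 = 27 infants already on treatment. This lowers the number of events to expect. It does not explain why only one direction is counted.

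**Conclusion.** The point holds in a limited form. All planned by-arm laboratory event counts face under-treatment. No table counts suppressed TSH or above-range FT4, and the significance rating is never summarized by arm. The AE tables cannot make up for this, because 15.1.1 keeps the values out of them.

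The size cannot be given as a number of children: the documents contain no event rates and, apart from the neonates, no split of the 31 by arm. The structural size is 0 of 2 over-treatment directions counted. The gap does not touch the LT4 dose comparison, and all efficacy analyses are already declared exploratory. It merits correction because it costs little and concerns the direction of harm that the protocol's background associates with liquid LT4.

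The conclusion assumes that laboratory ranges and ratings were recorded as protocol 15.1.1 requires. The relation of 15.1.1 to 17.2 and 17.3 is a secondary point of reconciliation.

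**What to change.** **SAP 10.1.** Add one descriptive table by arm on the SAF, with no test. It should show the number and percentage of children with at least one on-treatment value in each category:
- TSH below the laboratory's age-specific range, and TSH above it;
- FT4 above that range, and FT4 below it;
- TSH rated clinically significant, split high and low, and the same for FT4.

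Give as denominator the children with at least one on-treatment value and a recorded range. Show the number of samples per child, because follow-up visits give some children more chances of an out-of-range value. Mark the table as added after SAP 2.0.

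**Reconciliation.** State in the SAP or the clinical study report how 15.1.1 was applied alongside 17.2 and 17.3. List any child for whom a thyroid value alone met a seriousness criterion or was the reason for discontinuation, or state that there were none.

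**Cost.** One table from data already collected, and a check of the discontinuation reasons and the laboratory listing. The drawbacks are small numbers, local ranges that vary and are not always age-specific, and a rating made open-label without stated criteria. Footnotes can cover all three, and the range-based rows do not depend on the rating.
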